2.5.4 Sensitivity analyses

Sensitivity analyses for the two co-primary endpoints will be performed to examine robustness with respect to PDs based on the PPS.

To evaluate robustness of the analyses for the co-primary endpoint (change in BCVA from extension baseline at Week 52 and Week 56) that were based on the LOCF method, sensitivity analyses will be performed on the observed data in the FAS and MMRM. The MMRM model will include the change in BCVA as the dependent variable, age categories at baseline, BCVA categories at baseline, treatment arm in the core study, and assessment visit as the fixed effects and participant as a random effect.

2.6 Analysis of secondary objectives

The FAS will be used to analyze durability, functional, tolerability and anatomical outcomes.

2.6.1 Secondary endpoints

The following secondary endpoints evaluate the anatomical outcomes of brolocizumab in all participants and per randomized arm in the core study:

- Summary statistics of average change in CSFT from baseline of the extension study at Week 52 and Week 56 will be provided. In addition, equivalent summaries will be provided for participants who discontinued the study treatment early at the date of the last treatment and 4 weeks after.
- Summary statistics of average change in CSFT from baseline of the core study to Week 52 and Week 56 will be provided.
- Number (%) of patients with presence of IRF and/or SRF and sub-RPE fluid in the central subfield, as assessed by SD-OCT at Week 52 and Week 56 and by the number of visits will be provided. In addition, equivalent summaries will be provided for participants who discontinued the study treatment early at the date of the last treatment and 4 weeks after.

The following secondary endpoints evaluate the durability of brolocizumab in all participants and per randomized arm in the core study:

- Distribution of the duration of the last interval with no disease activity up to Week 56 will be provided.
- Distribution of the duration of the maximal intervals with no disease activity up to Week 56 will be provided.
- Distribution of the change of the duration of last interval with no disease activity between baseline of the extension study and Week 56 will be provided.

The following secondary endpoints evaluate the functional outcomes of brolocizumab per randomized arm in the core study:

- Summary statistics of the average change in BCVA from baseline of the extension study to Week 52 and Week 56 will be provided.

The following secondary endpoints evaluate the functional outcomes of brolocizumab in all participants and per randomized arm in the core study:

- Summary statistics of the change in BCVA from the baseline of the core study by visit will be provided. Boxplots with a trend line and the line plot of LSM (+/-SE) by visit will also be graphed.
- Summary statistics for the average change in BCVA from the baseline of the core study to Week 52 and Week 56 will be provided.

2.6.2 Statistical hypothesis, model, and method of analysis

Counts and proportions for the endpoints describing durability, tolerability, and anatomical outcomes (i.e., number of visits with presence of IRF and/or SRF) will be accompanied by 2-sided 95% CI inferred based on binomial distribution for each endpoint and 2-sided 95% simultaneous CIs inferred using the Goodman method (Goodman 1965). The Goodman method is used for obtaining simultaneous CIs (better than single binomial CIs) for the parameters of a multinomial distribution, for example for a multinomial endpoint (4-week interval, 8-week interval, 12-week interval, 16-week interval, and 20-week interval). These analyses will be performed for all participants and within the two regimens.

For the analyses of functional and anatomical outcome (i.e., change in CSFT) the 95% CI will be inferred based on ANOVA analyses. The same analysis model as used for change from

baseline in BCVA will be used with the baseline BCVA categories replaced by baseline CSFT categories.

2.6.3 Handling of missing values/censoring/discontinuations

In case of treatment interruption, if the duration of the last interval falls within the following ranges of [q4w, q8w) or [q8w, q12w), [q12w, q16w), [q16w, q20w) or \geq q20w then the floor value of these ranges i.e., q4w, q8w, q12w, q16w, q20w, respectively, will be used for imputation.

The last potential study treatment may be administered at the Week 52 visit (or at the Week 54 visit for the participants who will have received study treatment at an odd number of inspection visits). Hence throughout this document, analyses based on Week 52 BCVA and other efficacy data are performed if Week 52 data are available. If Week 52 BCVA and other efficacy data are not available, Week 54 BCVA and other efficacy data will be used instead of Week 52. Otherwise, LOCF will be used to impute missing BCVA as per the estimand framework.

For participants who discontinue study treatment but continue in the study, data collected after the switch to alternative treatment in the study eye will be censored for the primary analysis. Censored data will be replaced using LOCF with the last observation collected prior to/on the start of an alternative treatment in the study eye.

2.7 Safety analyses

The following endpoint will be used to assess the safety and tolerability of brolocizumab

- Occurrence of Ocular and Non-ocular AEs up to Week 56.

The primary population for safety analyses is the FAS. Additionally, the Enrollment Set will be used to summarize pre-treatment AEs and all AEs that occur during the extension study. All listings and tables will be presented for all participants.

Safety summaries (tables, figures) will include only data from the baseline of the extension study, which is also EOS/Week 64 of the core study.

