These impacts on the risk/benefit balance of the product are considered to be low and the overall risk/benefit assessment remains positive, when patients are dosed at q8w or longer after the loading phase and when patients who develop RV and/or RO are discontinued from further treatment with brolucizumab.

For further details, please refer to the investigator brochure (IB) or package insert whichever is applicable.

CRTH258A2303 study (TALON)

There is an ongoing study CRTH258A2303 (TALON) which intends to complement the current clinical dataset on brolucizumab by generating new evidence based on the T&E concept prevalent in the current management of patients with nAMD. It will be comparing the efficacy and safety of brolucizumab and aflibercept administered in three monthly injections at Baseline, Week 4, and Week 8 (loading phase), followed by an identical 4-week-adjustment Treat-to-Control regimen with treatment intervals from 8 to 16 weeks. Subjects requiring injections every 4 weeks after the loading phase will be discontinued from further study treatment.

This study, CRTH258A2303E1, is an extension study of the CRTH258A2303 (TALON) study, aiming at gathering additional long-term efficacy and safety evidence about brolucizumab in a TtC treatment regimen with treatment intervals further extended up to 20 weeks in nAMD. It intends to contribute to the growing clinical dataset of brolucizumab by generating supplementary evidence on treatment safety, efficacy, and durability in nAMD.

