1.2 Purpose

The purpose of this study is to evaluate the efficacy and safety of brolucizumab used in a Treat-to-Control (TtC) regimen with maximum treatment intervals up to 20 weeks for the treatment of patients with neovascular age-related macular degeneration (nAMD) who have completed the CRTH258A2303 study (TALON).

In addition, switch data from aflibercept to brolucizumab is collected.

2 Objectives and endpoints

Table 2-1 Objectives and related endpoints

Objective(s)	Endpoint(s)
Primary objective(s)	Endpoint(s) for primary objective(s)

To evaluate the extended durability of brolucizumab in a TtC regimen with respect to the duration of treatment intervals at Week 56	
Duration of the last interval with no DA up to Week 56

To evaluate the functional outcomes of brolucizumab in a TtC regimen with respect	
Change in BCVA from extension baseline at Week 52 and Week 56

Objective(s)	Endpoint(s)
to average change in BCVA at Week 52 and Week 56	
Secondary objective(s)	Endpoint(s) for secondary objective(s)

 To evaluate the anatomical outcomes of brolocizumab in all patients and per randomized arm in the core study To assess the durability of brolocizumab in all patients and/or per randomized arm in the core study To assess the functional outcomes of brolocizumab per randomized arm in the core study To assess the safety of brolocizumab 	
 Change in CSFT from extension baseline to Week 52 and Week 56 Number of visits with presence of IRF and/or SRF, and sub-RPE fluid in the central subfield, as assessed by SD-OCT at Week 52 and Week 56 Duration of the last interval with no DA up to Week 56 Duration of the maximal intervals with no DA up to Week 56 Change of the duration of last interval with no DA between extension baseline and Week 56 Change in BCVA from extension baseline to Week 52 and Week 56 Occurrence of Ocular and Non-ocular AEs up to Week 56

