2.2 Secondary estimands

Not applicable

3 Study design

This study is a 56-week, open-label, one-arm extension study in participants who have completed the CRTH258A2303 study (TALON).

[figure not shown]
Participants who consent and meet all the inclusion and none of the exclusion criteria will be enrolled into this extension study and receive brolocizumab 6 mg in a TtC regimen, irrespective of the treatment received in the core study.

Approximately 250 participants from the core study will enter the extension study. The maximum study duration for a participant is 56 weeks, including post-treatment follow-up.

There will be two periods in this study, see [Figure 3-1](#):

- Treat-to-Control treatment period: from Baseline (Day 1) to Week 52
- Post-treatment follow-up period: from Week 52 to Week 56.

Figure 3-1 Study design

Depending on visit schedules:

* 62 weeks (core) / 54 weeks (extension) ** Week 62 (core) / Week 54 (extension)

Baseline visit: Day 1

Participants should sign informed consent no later than the Week 64 (EOS) visit of the core study. Baseline visit for the extension study (extension baseline) should occur on the same day as the Week 64 (EOS) visit of the core study. Participants will be assessed on inclusion and exclusion criteria of the extension study at the baseline visit.

The study eye will be the same eye that received brolucizumab or aflibercept treatment in the core study.

Treat-to-Control treatment period: Day 1 to Week 52

All efforts should be made to adhere to the study visit schedule within a ± 14 day window (baseline visit should occur on the same day as the Week 64 (EOS) visit of the core study). For a given study visit, assessments can be performed on 2 consecutive days provided both days occur within the visit window. Study treatment is intended to be administered on the day of the study visit, or, if this is not possible, within 3 days after the assessments have taken place.

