5.2 Exclusion criteria

Patients fulfilling any of the following criteria at study entry are not eligible for inclusion in this study. No additional exclusions may be applied by the investigator, in order to ensure that the study population will be representative of all eligible patients.

1. Participant has a medical condition or personal circumstance which precludes study participation or compliance with study procedures, as assessed by the Investigator.
2. Participant has discontinued study treatment in the core study.
3. Anti-VEGF treatment is futile in the study eye, in the investigator's opinion.
4. Pregnant or nursing (lactating) women, where pregnancy is defined as the state of a female after conception and until the termination of gestation, confirmed by a positive human chorionic gonadotropin (hCG) pregnancy test.
5. Women of child-bearing potential, defined as all women physiologically capable of becoming pregnant, unless they are using highly effective methods of contraception during the study drug administration and for 3 months after stopping the investigational medication. Highly effective contraception methods include:

- Total abstinence (when this is in line with the preferred and usual lifestyle of the participant). Periodic abstinence (e.g., calendar, ovulation, symptothermal, post-ovulation methods) and withdrawal are not acceptable methods of contraception.
- Female sterilization (have had surgical bilateral oophorectomy with or without hysterectomy), total hysterectomy, or tubal ligation at least six weeks before taking study treatment. In case of oophorectomy alone, only when the reproductive status of the woman has been confirmed by follow up hormone level assessment.
- Male sterilization (at least 6 months prior to baseline). For female participants on the study, the vasectomized male partner should be the sole partner for that participant.
- Use of oral (estrogen and progesterone), injected or implanted hormonal methods of contraception or placement of an intrauterine device (IUD) or intrauterine system (IUS), or other forms of hormonal contraception that have comparable efficacy (failure rate < 1%), for example hormone vaginal ring or transdermal hormone contraception.

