12.5.2 Safety endpoints

The following endpoints assess the safety of brolocizumab

- Occurrence of Ocular and Non-ocular AEs up to Week 56

For all safety analyses, the FAS will be used. All listings and tables will be presented in all participants.

Safety summaries (tables, figures) include only data from the on-treatment period with the exception of baseline data which will also be summarized where appropriate (e.g. change from baseline summaries). In addition, a separate summary for death will be provided. In particular, summary tables for adverse events (AEs) will summarize only on-treatment events, with a start date during the on-treatment period. A separate summary table will be provided for AEs of study eye, fellow eye and non-ocular AEs.

The on-treatment period lasts from the date of first administration of study treatment to 30 days after the last administration of study treatment (EOT) or EOS whichever is the latest.

Adverse events

Treatment emergent AEs are defined as AEs which start on or after the time of the first injection of study treatment in this extension study and until the patient exits the study. AEs which start prior to the date/time of the first injection of study treatment in this extension study will be listed only. Treatment emergent AEs occurring during the last 6 months of the core study, for the same set of participants included in the extension study safety set will be presented. All treatment emergent SAEs/AEs as documented in the core study will be listed as medical history.

The number (and percentage) of participants with treatment emergent adverse events (events started after the first dose of study medication or events present prior to start of the extension study but increased in severity based on preferred term) will be summarized in the following ways:

- by primary system organ class and preferred term.
- by primary system organ class, preferred term and maximum severity.
- by Standardized MedDRA Query (SMQ) and preferred term.

Separate summaries will be provided for study medication related adverse events, death, serious adverse events, other significant adverse events leading to discontinuation.

[figure not shown]
The number (and proportion) of participants with adverse events of special interest will be summarized.

A participant with multiple adverse events within a primary system organ class is only counted once towards the total of the primary system organ class.

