2.3 Patient disposition, demographics and other baseline characteristics

Demographic and other extension study baseline data including disease characteristics will be summarized by appropriate descriptive statistics for all analyses sets. A listing will also be provided.

A baseline (of the extension study) disease characteristic table will be provided by treatment groups of the core study and overall, including:

- Primary diagnosis of nAMD, time since diagnosis of nAMD (days), whether nAMD is unilateral or bilateral and intraocular pressure (IOP).
- BCVA (as a continuous variable and using categories (< 55, 55-< 73, ≥ 73 letters read)),
- OCT angiography parameters – if collected.
- SD-OCT parameters (IRF, SRF, sub-RPE, CSFT (as a continuous variable and using categories (< 400, ≥ 400 μm)) and lesion type).
- CFP parameters (intra-retinal hemorrhage – central subfield, sub-retinal hemorrhage – central subfield, RPE atrophy – outer subfield, RPE atrophy – central subfield, fibrosis – inner subfield, fibrosis – central subfield).
- FA parameters (type of CNV, area of CNV within the lesion, CNV location, leakage from CNV).

Relevant medical histories and current medical conditions at baseline of the extension study will be summarized separately by system organ class and preferred term for the FAS.

Medical history/current medical conditions will be coded using the latest version of Medical Dictionary for Regulatory Activities (MedDRA) terminology available at the time of the analyses. The MedDRA version used for reporting will be specified in the clinical study report (CSR) and as a footnote in the applicable tables/listings.

Medical histories which started before the core study and are ongoing on Day 1 of the extension study will be recorded on the Medical History eCRF. Data collected for the Medical History

eCRF for the extension study will be presented by the treatment arm in the core study and overall. Columns will be included to identify if the event started before the core study, during the core study, or during the extension study; and if the event is ongoing or ended during the Extension study.

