All deaths, SAEs or AEs leading to permanent study treatment discontinuation during the study will be summarized.

Adverse events are coded using MedDRA terminology.

For the legal requirements of ClinicalTrials.gov and EudraCT, two tables are mandatory:

- <on-treatment/treatment emergent> adverse events which are not serious adverse events with an incidence greater than X%. Detailed threshold (X%) will be determined by safety disclosure
- <on-treatment/treatment emergent> serious adverse events and SAE suspected to be related to study treatment will be provided by system organ class and preferred term on the safety set population.

If for a same patient, several consecutive AEs (irrespective of study treatment causality, seriousness and severity) occurred with the same SOC and PT:

- a single occurrence will be counted if there is ≤ 1 day gap between the end date of the preceding AE and the start date of the consecutive AE
- more than one occurrence will be counted if there is > 1 day gap between the end date of the preceding AE and the start date of the consecutive AE

For occurrence, the presence of at least one SAE / SAE suspected to be related to study treatment / non-SAE has to be checked in a block e.g., among AE's in a ≤ 1 day gap block, if at least one SAE is occurring, then one occurrence is calculated for that SAE.

The number of deaths resulting from SAEs suspected to be related to study treatment and SAEs irrespective of study treatment relationship will be provided by SOC and PT.

2.7.1.1 Adverse events of special interest / grouping of AEs.

The number (%) of subjects with treatment-emergent AESIs will be summarized by category and PT.

A Case Retrieval Sheet (CRS) with the exact composition of the AE groupings is to be used to map reported AEs to the AESI groupings. This file may be updated (i.e., it is a living document) based on review of accumulating trial data, and therefore the groupings are also subject to potential change. The most up-to-date version of the CRS will be used at the time of the analysis.

AESIs related to the study treatment and/or study treatment procedure will be summarized by category and PT term.

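### Safety tables are planned only for all participants pooled, so any difference in inflammation risk between those switched from aflibercept and those already on brolucizumab would not be shown

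*SAP*

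**What the plan says.** **Safety is pooled.** SAP 2.7: "All listings and tables will be presented for all participants". Protocol 12.5.2: "All listings and tables will be presented in all participants". The AESI summary in SAP 2.7.1.1 follows the same pattern: "The number (%) of subjects with treatment-emergent AESIs will be summarized by category and PT". The TEAE, pre-treatment, study-emergent, death and BCVA-loss summaries in SAP 2.7.1 to 2.7.3 have no core-arm breakdown either.

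**Core arm is used elsewhere.** In SAP 2.3 the baseline disease characteristics "table will be provided by treatment groups of the core study and overall", and medical history is shown the same way. SAP 2.4.2 shows prior ocular medications by core arm. SAP 2.6.1 plans anatomical, durability and functional outcomes per randomized core arm. SAP 2.5.2 puts core arm into the primary BCVA model as a fixed effect.

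**The population is mixed.** On the core study, protocol 1.1 says: "It will be comparing the efficacy and safety of brolucizumab and aflibercept". In the extension, participants "receive brolocizumab 6 mg in a TtC regimen, irrespective of the treatment received in the core study" (protocol Section 3). Exclusion criterion 2 is: "Participant has discontinued study treatment in the core study". Protocol 1.2 adds a further purpose, collecting data on the change of drug: "In addition, switch data from aflibercept to" brolucizumab.

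**The mechanism is stated.** Protocol 1.1 and 4.5 report a causal link between a treatment-emergent immune reaction to brolucizumab and retinal vasculitis and/or occlusion, typically with intraocular inflammation.

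**The concern.** The two core arms enter the extension with different histories. Former aflibercept participants meet study brolucizumab in the study eye for the first time. Former brolucizumab participants have been through a 64-week core study on the drug, and those who stopped treatment there cannot enter. Because the harm of interest is described as an immune reaction that emerges on treatment, equal risk in the two groups is not a safe default.

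If the risks differ, a single pooled AESI percentage is a weighted average that may match neither group. Its value would change with the proportion of switchers enrolled even if nothing about the drug changed. No planned safety table would describe the switch from aflibercept, although data on it are collected as a stated purpose.

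A related point concerns the TEAEs from the last 6 months of the core study, which protocol 12.5.2 says will be presented for the same participants. Unsplit, that display would mix aflibercept and brolucizumab exposure. SAP 2.7 does not carry it over.

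**Working it through.** **1. The plan's own precision figure.** The documents state no expected inflammation rate for this study and no precision for safety. The nearest planning figure is the 95% CI width for the 20-week proportion in protocol 12.8. The Wald width is 2 × 1.96 × √(p(1−p)/n). With p = 0.194 and n = 250 it is 2 × 1.96 × √(0.194 × 0.806 / 250) = 9.8%, as stated. This confirms the planned N but does not bear on the pooling.

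**2. Inputs for an illustration.**
- N is about 250 (protocol Sections 3 and 5).
- The split by core arm is not stated. Assumed 50:50, so about 125 per arm; range 40:60 to 60:40.
- Risk by prior exposure is not stated. Assumed 3-4.5% in newly exposed and 0.5-1% in previously treated participants. The nearest documented rates are 5.3% in females and 3.2% in males in HAWK and HARRIER (protocol 4.5), midpoint (5.3 + 3.2)/2 = 4.25%. The 0.5-1% has no source in the documents.

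**3. Pooled rate.** Pooled = w × p_new + (1 − w) × p_prior, with w = 0.5:

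| Newly exposed | Previously treated | Pooled | Pooled relative to newly exposed |
|---|---|---|---|
| 3% | 0.5% | 1.75% | 42% lower |
| 3% | 1% | 2.00% | 33% lower |
| 4.5% | 0.5% | 2.50% | 44% lower |
| 4.5% | 1% | 2.75% | 39% lower |
| 4.25% | 4.25% | 4.25% | equal |

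The pooled range is 1.75-2.75%. The last row shows that the gap vanishes if the risks are equal.

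**4. Dependence on arm mix.** With 4.25% and 1%:
- w = 0.4: 0.4 × 4.25 + 0.6 × 1 = 2.30%
- w = 0.5: 0.5 × 4.25 + 0.5 × 1 = 2.63%
- w = 0.6: 0.6 × 4.25 + 0.4 × 1 = 2.95%

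The reported rate moves although neither group's risk has changed.

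**5. What a split could show.** Exact (Clopper-Pearson) 95% CIs:
- 3/125: 0.5% to 6.9%
- 5/125: 1.3% to 9.1%
- 1/125: 0.02% to 4.4%
- 6/250 pooled: 0.9% to 5.2%

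Power to detect 4.25% against 1% with 125 per arm is about 36%. The split can describe the groups but cannot test a difference.

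**The case against.** The strongest reply is that pooling matches the stated objective. Table 2-1 attaches core arm to the anatomical, durability and functional objectives, while the safety objective is simply to assess safety. Amendment 1 deliberately removed a by-treatment presentation from protocol 12.5.2 because the study has one arm. This stands: the request is for an added display and does not correct a broken commitment. A reader might infer from protocol 1.2 that a by-arm safety analysis was promised, but that text says only that switch data are collected.

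A reader might also infer that the pooled rate certainly understates risk in new users. The documents do not support that:
- No rate by prior exposure is given.
- The HAWK and HARRIER rates come from regimens with three monthly loading doses, which the extension does not have.
- Exclusion criterion 2 applies to both core arms. Under the extension's rules, inflammation without vasculitis or occlusion does not force discontinuation. If the core study had the same rule (its protocol is not available here), some participants with prior inflammation could have rolled over.

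Nor can one say that safety was the main concern behind both amendments. Amendment 1 was safety-driven. Amendment 2 gives sample size reduction as its main purpose, although that followed from a safety measure.

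Part of the gap may be covered elsewhere. SAP 2.6.2 names tolerability among analyses done within two regimens, but SAP 2.6.1 lists no tolerability endpoint, the two regimens are undefined in a one-arm study, and the specific rule in SAP 2.7 says all participants. The table shells are a separate document, and any exploratory sections are not visible, so a by-arm safety output there cannot be ruled out.

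**Conclusion.** The point holds in conditional form. Both documents pool safety by explicit rule, while core arm is used for baseline characteristics, medical history, efficacy and the primary BCVA model. The immune mechanism makes a difference by prior exposure plausible, and the plan as written would not show one. If risk differs, the pooled AESI rate describes neither group; if it does not, nothing is lost. Under the assumed 50:50 mix and assumed risks, the pooled rate of 1.75-2.75% lies 33-44% below the newly exposed rate. These figures illustrate the mechanism and are not estimates for this trial. No primary or secondary endpoint is affected, so this is a worthwhile, inexpensive improvement to the safety reporting.

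**What to change.** In SAP 2.7, 2.7.1, 2.7.1.1 and 2.7.3, add columns by core randomized arm beside the overall column for:
- study-eye ocular TEAEs;
- TESAEs;
- AESIs, with exact 95% CIs;
- loss of ≥15 and ≥30 letters in BCVA.

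Label the split descriptive, with no formal comparison. Reword the all-participants rule in SAP 2.7 to match, and reconcile it with the undefined reference to two regimens in SAP 2.6.2.

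The cost is two extra columns in tables that already exist. No new data or participants are needed, and the core-arm codes are already required for the primary BCVA model and the per-arm efficacy summaries. Core randomization data stay confidential until database lock (protocol 6.4) and the primary analysis follows lock (SAP 1.1), so masking is unaffected. The downside is small cells with wide intervals, which readers must not take as evidence for or against a difference between arms.
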